**Table 1: Visit Window**

Analysis Visit	Relative Target Day	Analysis Visit Window (Study Days)	
		eGFR and Safety Labs	Quantitative Urinalysis
Week 2	15	2 – 22	N/A
Week 4	29	23 – 57	2 – 57
Week 12	85	58 – 127	58 – 127
Week 24	169	128 – 183	128 – 183
Week 28	197	>183	>183

eGFR = estimated glomerular filtration rate; N/A = Not applicable

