1.3. Schedule of Activities (SoA)

| | Screening | Baseline | Study Treatment Period | | | | Safety Follow-up Visit |
|--|---|----------|------------------------|----------|----------|-----------------|-----------------------------|
| Week | -- | Day 1 | Week 2 | Week 4 | Week 12 | Week 24/ EOT | Week 28/4-week Safety Visit |
| Visit | 1 | 2 | 3 | 4 | 5 | 6 | 7 |
| Visit Window | Day -42 to Day -1 | -- | ± 5 days | ± 7 days | ± 7 days | ± 7 days | ± 7 days |
| Informed Consent | X | | | | | | |
| Inclusion/Exclusion | X | | | | | | |
| Screening Tests ^a | X | | | | | | |
| IRT | X | X | | | | | |
| Medical History | X | | | | | | |
| Demographics | X | | | | | | |
| Peripheral Edema Assessment ^b | X | X | X | X | X | X | X |
| Vital Signs ^c | X | X | X | X | X | X | X |
| Clinical Laboratory Assessments ^d | X | X | X | X | X | X | X |
| Lipid Panel ^e | X | X | | | X | X | |
| Physical Examination ^f | X | X | X | X | X | X | X |
| Adverse Event Assessment | -----Continuous Monitoring----- | | | | | | |
| Concomitant Medications/Therapies | -----3 Months prior to screening followed by Continuous Monitoring----- | | | | | | |
| RAAS Inhibitor Treatment ^g | X | | | | | X | |
| SGLT2 Inhibitor Treatment | -----Continuous Treatment----- | | | | | | |
| Quantitative urinalysis | X | X | | X | X | X | X |
| Calculate eGFR ^h | X | X | X | X | X | X | X |
| Study Intervention Dispensing | | X | X | X | X | | |
| Study Intervention Accountability | | | X | X | X | X | |
| Pregnancy Test ⁱ | X | X | X | X | X | X | X |
| Dispense Urine Pregnancy Test ^j | | | | X | X | | |

Abbreviations: ALP = alkaline phosphatase; ALT = alanine transaminase; AST = aspartate aminotransferase; BP = blood pressure; BUN = blood urea nitrogen; eGFR = estimated glomerular filtration rate; EOT = end of treatment;

HDL = high-density lipoprotein; IRT = interactive response technology system; LDL = low-density lipoprotein; MCH = mean corpuscular hemoglobin; MCHC = mean corpuscular hemoglobin concentration; MCV = mean corpuscular volume; pH = potential for hydrogen; RAAS = renin-angiotensin-aldosterone system; SOC = standard of care; SGLT2 = sodium glucose cotransporter-2; WBC = white blood cell.

- a Includes plasma follicle stimulating hormone level (to confirm menopausal status only).
- b Peripheral edema assessment guidance provided in [Section 10.4](#).

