4. STUDY DESIGN

4.1. Overall Design

This is a 28-week, open-label, multicenter, single-group Phase 2 exploratory study to determine the safety and effect of sparsentan in participants with IgAN who are at risk of disease progression despite being on both stable RAASi and SGLT2 inhibitor treatment for at least 12 weeks prior to study entry.

Participants who provide written informed consent will be assessed for eligibility and will undergo baseline evaluations including clinical laboratory tests. Per the eligibility criteria, all participants are required to be on a stable dose(s) of ACEI and/or ARB therapy and on a stable dose of a SGLT2 inhibitor at screening and will continue their stable treatments through the screening period. Eligible participants entering the study will remain on the stable dose of the SGLT2 inhibitor for the duration of the study, however, they will discontinue ACEI and/or ARB therapy before the Day 1 visit. The final dose of an ACEI and/or ARB therapy should be taken on the day before the Day 1 visit. Baseline evaluations will be taken on Day 1 prior to administration of the first dose of the study intervention (sparsentan) according to [Section 6.1](#).

Study visits will be conducted at weeks 2-, 4-, 12-, and 24- following Day 1. Following the 24-week treatment period, study intervention will be discontinued for 4 weeks. At this time, the Investigator should resume standard of care treatment, including RAAS inhibitor treatment. Participants will return to the site for a visit at Week 28 for the safety follow-up visit.

UA/C and UP/C will be determined using first morning void (FMV) samples and will be calculated as the average of 2 FMV samples collected within 3 days prior to each visit. If 1 of the samples is missing, UA/C and UP/C from the single sample will be used.

The overall study design is summarized in [Figure 1](#). For individual participants, the total duration of participation from the screening visit to the safety follow-up visit (Week 28) will be a maximum of 34 weeks.

Specific procedures to be performed during the study, as well as their prescribed times and associated visit windows are outlined in the SoA in [Section 1.3](#). Details of each procedure are provided in [Section 8](#).

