### 6.5.3. Visit Windows

A visit window method will be applied to determine the record to be used for analysis across the study period for efficacy and safety endpoints based on laboratory results, including eGFR and quantitative urinalysis (including UP/C and UA/C). If a patient has multiple assessments (including unscheduled visits) within the visit window, the value closest to the target day for that visit will be selected for analysis. If more than 1 assessment is equidistant to the target day, then latest value will be selected.

The visit window shown in Table 1 is defined for endpoints based on laboratory results.

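### SAP Table 1 counts Day 22 as Week 2 for eGFR and safety labs, although Day 22 is the first day the protocol allows for the Week 4 visit

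*SAP*

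**What the plan says.** **Protocol.** Visit weeks are counted from Day 1 (section 4.1: "Study visits will be conducted at weeks 2-, 4-, 12-, and 24- following Day 1"). The visit-window row of the Schedule of Activities (section 1.3) begins "Day -42 to Day -1 | -- | ± 5 days | ± 7 days". Its entries are, in order, screening, Day 1, Week 2 and Week 4. The later visits also carry 7 days either way. The same schedule calls for eGFR at every visit: "Calculate eGFR ^h | X | X | X | X | X | X | X". Clinical chemistry and hematology are also drawn at every visit.

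**SAP.** Section 6.5.3 assigns laboratory records to visits by study day. When several fall in one window, "the value closest to the target day for that visit will be selected for analysis". Ties are settled by the sentence "If more than 1 assessment is equidistant to the target day, then latest value will be selected". The two rows of Table 1 at issue are "Week 2 15 2 – 22 N/A" and "Week 4 29 23 – 57 2 – 57". The columns are visit, target day, window for eGFR and safety labs, and window for quantitative urinalysis. Section 6.6 rules out imputation of missing values. Neither document assigns a laboratory record by its nominal visit.

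**The concern.** The two documents disagree about one day. Under the protocol, a participant seen on Day 22 can only be at an in-window Week 4 visit. Under Table 1, that day's blood results belong to Week 2. The urine for the same visit is analysed as Week 4, because the urine window runs from Day 2 to Day 57, so one visit carries two labels.

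Change in eGFR at each visit is a secondary endpoint, and SAP section 8.2.2.2 reports both descriptive summaries and model estimates by visit. Week 4 is also the first scheduled laboratory visit after the planned dose increase at Week 2, and the protocol's risk table names acute kidney injury, hyperkalemia and transaminase elevation. A correctly timed Week 4 result should not leave the by-visit tables because of where a boundary was drawn.

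**Working it through.** **1. How Table 1 was built.** The target days are 15, 29, 85, 169 and 197. The midpoints of neighbouring targets are:

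- (15 + 29)/2 = 22
- (29 + 85)/2 = 57
- (85 + 169)/2 = 127
- (169 + 197)/2 = 183

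These are exactly the upper limits in Table 1. The midpoint day always goes to the earlier visit.

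**2. Allowed visit days against Table 1 (eGFR and safety labs).** Allowed days are the target plus or minus the protocol tolerance.

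| Visit | Target | Tolerance (days) | Allowed days | Table 1 window | Allowed days outside own window |
|---|---|---|---|---|---|
| Week 2 | 15 | 5 | 10–20 | 2–22 | none |
| Week 4 | 29 | 7 | 22–36 | 23–57 | Day 22 |
| Week 12 | 85 | 7 | 78–92 | 58–127 | none |
| Week 24 | 169 | 7 | 162–176 | 128–183 | none |
| Week 28 | 197 | 7 | 190–204 | >183 | none |

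Weeks 2 and 4 are 14 days apart, so a tolerance of 7 days reaches the midpoint exactly. The other gaps are 28 days or more, and there it does not.

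**3. What happens to a Day 22 result.** Its distance from the Week 2 target is |22 − 15| = 7 days. An in-window Week 2 result on day d (10 to 20) has |d − 15| ≤ 5, so it is selected in all 11 cases and the Day 22 result is assigned to no visit. A sample on Day 9 or Day 21 (distance 6) would also win. The Day 22 result is kept only if every other sample in the window lies on Days 2 to 8 or there is none; Day 8 ties at 7 days and the later value is taken. In that case it is reported as Week 2.

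**4. What happens to Week 4.** Unscheduled samples count, so any sample on Days 23 to 57 fills Week 4. Otherwise it stays missing.

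**5. Size.** One of 15 allowed days is affected. The documents give no distribution of visit days, so the number of participants is an assumption, taking all 60 to attend Week 4:

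- Visits clustered near Day 29: about 0 to 2 of 60. The upper figure corresponds to 2/60 = 3.3% of visits falling exactly 7 days early.
- Visits spread evenly over the window: 1/15 = 6.7%, and 60 × 1/15 = 4.

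**6. Check of the change.** With Week 2 = Days 2–21 and Week 4 = Days 22–57, all allowed days in the table above fall in their own window. A late, out-of-window Week 2 sample on Day 22 would enter Week 4 but could not displace an in-window Week 4 sample on Days 23 to 36. That sample is closer to Day 29 or, on Day 36, equally close and later.

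**The case against.** The best defence is that Table 1 contains no arithmetic error. It follows one midpoint convention throughout, Day 22 is equally far from both targets, and any convention has to put it somewhere. That is right about the construction. It does not settle which side the day belongs on: the protocol allows a Week 4 visit on Day 22 and does not allow a Week 2 visit then.

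The other objections limit the point, and they stand.

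- **A reader might infer that the result is lost, and a potassium or liver signal with it.** The documents do not support this. All collected data are listed. The shift tables in SAP sections 9.5.1 and 9.5.2 use worst and last values, scheduled or not. Liver abnormalities (9.5.3) and NT-proBNP elevations (9.5.4) are counted over the whole study. Only by-visit outputs and the eGFR model lose the value.
- **A reader might infer that the primary result is affected.** It is not. UA/C and UP/C use the Day 2–57 window, and Table 1 does not govern blood pressure. The modelled eGFR change is from baseline to Week 24, and one missing intermediate value in a few participants should move it little. The study is descriptive, with no hypothesis test.
- **A reader might infer that this is the only boundary that can mislabel a visit.** That holds only for visits timed from Day 1. The protocol also times the safety follow-up from the last dose. A last dose on Day 60 puts follow-up near Day 88, which Table 1 labels Week 12. A last dose on Day 162, with follow-up 28 days later and 7 days early, gives 162 + 28 − 7 = Day 183, which Table 1 labels Week 24.

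**Conclusion.** The point holds as a one-day conflict between the protocol schedule and SAP Table 1, confined to eGFR and safety laboratory results. A compliant Week 4 sample on Day 22 is labelled Week 2. It is left out of the by-visit outputs whenever a Week 2 result lies closer to target, and otherwise reported under the wrong visit.

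The conflict itself rests only on the stated targets and tolerances, with Week 4 taken as Day 29 as in the SAP. The number of participants rests on an assumed spread of visit days: 0 to 2 of 60 is the more plausible range and may be zero, and 4 of 60 requires an even spread. This is a minor correction. No conclusion of the study depends on it.

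**What to change.** In Table 1, change the column for eGFR and safety labs to Week 2 = Days 2–21 and Week 4 = Days 22–57. Leave the urine windows as they are. No in-window Week 2 visit is harmed, since the last allowed day is Day 20.

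The cost is two numbers in a SAP revision before analysis, with no protocol amendment and no new data. If the SAP is not revised, a departure from Table 1 would have to be documented in the clinical study report, as SAP section 2 requires. The change does not deal with safety follow-up visits timed from an early last dose, which can still fall in an earlier visit's window.

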## 6.6. Handling of Missing Data

The study will have processes and procedures in place to minimize missing data and to collect information on participants even after discontinuing study medication. Missing values will not be imputed.

### 6.6.1. Primary Analysis

UA/C and other quantitative urinalysis measures such as UP/C will be determined using FMV samples and will be calculated as the average of 2 FMV samples collected within 3 days prior to each visit. If 1 of the samples is missing, UA/C and UP/C from the single sample will be used.

## **6.6.2. Local Laboratories**

The primary analyses will use central laboratory data only. As a sensitivity analysis, local laboratory data may be included with central laboratory data.

## **6.6.3. Missing Adverse Event or Concomitant Medication Onset Date**

AEs and concomitant medications with incomplete onset dates will be assumed to have started during the study in accordance with the following prioritized list of assumptions:

1. Missing year: event or medication assumed to have the same year as first dose of study medication or year of end date, whichever is earlier.
2. Missing month: event or medication assumed to have started during the study if the year is the same or later than the year of the first dose of study medication. Event or medication assumed to have started at the same month of the first dose of study medication or same month as end date (if year of end date  $\leq$  year of event), whichever is earlier.
3. Missing day: event or medication assumed to have the same day as first dose of study medication if the year and month of onset are the same as year and month of first dose of study medication or the same day as end date, whichever is earlier. Otherwise, the day is assumed to be the first of the month.

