Planned maximum duration for each participant in this study is 34 weeks.

- Screening period of up to 6 weeks.
- Treatment period of 24 weeks.
- Safety follow-up visit 4 weeks after the final dose.

Key Eligibility Criteria

For a full list of eligibility criteria, please refer to [Section 5](#).

Inclusion Criteria

- Participant aged ≥ 18 years at the time of signing the informed consent.
- Participant has biopsy-proven IgAN. The biopsy may have been performed at any time in the past.
- Participant has a UA/C ≥ 0.3 g/g at screening.
- Participant has an eGFR value of ≥ 25 mL/min/1.73m² at screening.
- The participant has been on a stable dose of an SGLT2 inhibitor for at least 12 weeks prior to screening.
- Participant has been on a stable dose of ACEI and/or ARB therapy for at least 12 weeks prior to screening that is:
 - The participant's maximum tolerated dose (MTD), and
 - at least one half of the maximum labeled dose (MLD)

Exclusion Criteria

- Participant has IgAN secondary to another condition or immunoglobulin A (IgA) vasculitis.
- Participant has undergone any organ transplant, with the exception of corneal transplants.
- Participant has a documented history of heart failure, clinically significant cardiovascular or liver disease.
- Participant has been taking high dose (defined as >10 mg/day prednisone) or other any systemic immunosuppressive medications within 12 weeks of prior to screening.

Statistical Considerations:

Sample Size Justification

To investigate the safety and effect of sparsentan in participants with IgAN on chronic stable treatment with an SGLT2 inhibitor, approximately 60 participants will be enrolled in the study. The sample size of the study is determined empirically without formal statistical assumptions. A sample size of 60 is sufficient to detect at least one adverse event with probability 95%, assuming an expected adverse event incidence of 5% using the binomial distribution.

Analysis Sets

Full Analysis Set (FAS): All participants who take at least 1 dose of sparsentan will be included in the FAS. All efficacy analyses will be based on the FAS.

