## **6.6.4. Missing Adverse Event or Concomitant Medication End Date**

If the entire end date is unknown and the event or concomitant medication is not considered ongoing at the end of study or follow-up, the event or medication will be assumed to have ended on the last date of contact for the patient.

If only the day of end date is unknown, the day will be assumed to be the last of the month or the last date of contact for the patient, whichever is earlier.

If both the day and month of end date are unknown, the event or medication will be assumed to have ended on the last day of the year or the last date of contact for the patient, whichever is earlier.

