### 9.1. Adverse Events

AE data will be collected from the time that signed informed consent is obtained until the patient fully completes his/her participation in the study.

All AE summaries will be restricted to TEAEs, which are defined as any AE that newly appears, increases in frequency, or worsens in severity following the initiation of study medication, occurring during the treatment period. If it cannot be determined whether the AE is treatment-emergent due to a partial onset date, then it will be counted as treatment-emergent. Verbatim terms will be coded to PTs and SOC using MedDRA version 26.0.

Summaries that are displayed by SOC and PT will be ordered by descending order of incidence of SOC and PT within each SOC. Summaries of the following types will be presented:

- Overall summary of TEAEs.
- Patient incidence of TEAEs and the total number of entries by SOC and PT.
- Patient incidence of TEAEs and the total number of entries by PT in descending order.
- Patient incidence of TEAEs by SOC, PT, and highest severity. At each level of patient summarization, a patient is classified according to the highest severity if the patient reported 1 or more events. AEs with missing severity will be considered severe for this summary.
- Patient incidence and total number of entries of severe TEAEs by SOC and PT. AEs with missing severity will be considered severe for this summary.
- Patient incidence and total number of entries of study medication (Sparsentan) related TEAEs by MedDRA SOC and PT. Related AEs are those with relationships reported as “Possibly Related” or “Related”. AEs with a missing relationship will be considered related for this summary.
- Patient incidence and total number of entries of SGLT2 inhibitor related TEAEs by MedDRA SOC and PT. Related AEs are those with relationships reported as “Possibly Related” or “Related”. AEs with a missing relationship will be considered related for this summary.
- Patient incidence of serious TEAEs and the total number of entries by SOC and PT.
- Patient incidence of TEAEs leading to treatment discontinuation by SOC and PT.
- Patient incidence and total number entries of treatment-emergent AEOIs by SOC and PT.
- Patient incidence and total number of entries of TEAEs associated with safety topics of interest by PT.

- Patient incidence and total number of entries of related TEAEs associated with safety topics of interest by PT.

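### SAP 6.6.3 can impute an onset date after the participant has left the study when the onset year follows the first-dose year and the month is missing, and the SAP does not say whether that date or the SAP 9.1 fallback decides treatment emergence

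*SAP*

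**What the plan says.** SAP 6.6.3 opens by placing every incomplete onset within the study. For a missing month it repeats that intent: the event or medication is "assumed to have started during the study if the year is the same or later than the year of the first dose". The operative rule follows: "Event or medication assumed to have started at the same month of the first dose of study medication", or in the month of the end date. The earlier of the two applies, and the end-date month is used only if the end-date year is not after the event year. The day is then set. When the year and month differ from those of first dose, "Otherwise, the day is assumed to be the first of the month", unless an end date limits it. Nothing in the section caps the imputed onset at last dose or last contact.

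SAP 6.6.4 handles end dates. If the end date is wholly unknown and the event is not ongoing, "the event or medication will be assumed to have ended on the last date of contact for the patient". An ongoing event gets no imputed end date. The SAP does not say whether end dates are imputed before onset dates.

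SAP 9.1 restricts all AE summaries to events that arise or worsen "following the initiation of study medication, occurring during the treatment period". It adds a fallback: "If it cannot be determined whether the AE is treatment-emergent due to a partial onset date, then it will be counted as treatment-emergent".

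On duration, the protocol synopsis states: "Planned maximum duration for each participant in this study is 34 weeks". This is up to 6 weeks of screening, 24 weeks of treatment and 4 weeks of follow-up.

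**The concern.** The first-dose month is a sensible conservative choice when the onset year equals the first-dose year, because it places the event at the start of treatment. The same month in the following year is roughly a year after first dose, in a study that follows each participant for about 28 weeks from Day 1. The rule then yields the opposite of what its own section says it assumes.

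Two things are at stake. First, a listing could show an onset after the participant's last contact, which is impossible. Second, 6.6.3 turns a partial date into a complete one. A program that compares the completed date with the treatment period would find the event outside it, and the 9.1 fallback, which is triggered by a partial date, might never be reached. The result would be an undercount of treatment-emergent events, from a rule meant to err the other way.

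**Working it through.** The plan states no figure for the imputed date, so there is none to reproduce. The check is calendar arithmetic on the written rule.

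**Inputs**
- Treatment lasts 24 weeks (SAP 4.1). The Week 24 target is Day 169 and the Week 28 target is Day 197 (SAP Table 1).
- The Week 28 visit window is ±7 days (Protocol 1.3), so the latest in-window final visit is 197 + 7 = Day 204.
- Imputed onset is the 1st of the first-dose month in the reported year (SAP 6.6.3, no usable end date).
- Study day = imputed date − first-dose date + 1.
- First-dose years 2022 to 2024 are assumed, for illustration only.

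**1. No earlier end date.** Call the first-dose year Y and the reported onset year Y+1. Follow-up to Day 204 reaches Y+1 for first doses from 12 June to 31 December. Over all those dates the imputed onset is study day 336 to 367 (48.0 to 52.4 weeks). The smallest value comes from a first dose on the 31st of a month, the largest from a first dose on the 1st with a leap day in between. Every value exceeds Day 204, by at least 336 − 204 = 132 days.

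Example: first dose 15 September 2023, onset recorded as 2024 only, ongoing. The imputed onset is 1 September 2024, Day 353. Week 24 is 1 March 2024 (Day 169).

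**2. With a recorded end date.** Same participant, end date 20 February 2024. February is earlier than September, so the rule gives February 2024: Day 140 if the 1st is used, Day 159 if the 20th. Both are before Day 169. An end date in Y+1 and within follow-up always has an earlier calendar month than first dose, because follow-up spans only 203 days after Day 1. The failure is therefore confined to events without a usable end date.

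**3. Treatment emergence under SAP 9.1, read on the raw partial date.**
- Treatment ran into Y+1: the year alone cannot show whether onset was on or after treatment, so the fallback counts the event.
- Treatment ended before Y+1: onset is after treatment whatever month is imputed, so 6.6.3 changes nothing.

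The first case needs Day 169 to fall in Y+1, that is, first dose from 17 July to 31 December: 168 dates. With uniform enrolment (assumed), 168/365 = 46%.

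**4. With 1 January of Y+1 imputed instead.**
- First dose 17 July to 31 December: imputed Day 169 down to Day 2, within the planned span to Week 24.
- First dose 12 June to 16 July: imputed Day 204 down to Day 170, after treatment but still within follow-up.
- The September example becomes Day 109 instead of Day 353.

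**The case against.** The strongest reply is that SAP 9.1 already protects the TEAE tables. An event known only by a year that treatment reached cannot be classified from its partial date, so the fallback counts it. No text tells the programmer to test the imputed date first, and 6.6.3 itself states the intent that the onset is within the study. A reader might infer that the rule removes events from the TEAE tables; the documents do not support that. A loss needs a programming order that the SAP neither requires nor rules out.

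Other limits also stand. A recorded end date within follow-up brings the imputed month back. If end dates are imputed first, the last-contact date in 6.6.4 does the same for non-ongoing events whose end date is wholly unknown. An imputed onset later than an imputed end date therefore arises only under the other order. For medications, SAP 9.4 asks only whether the start was before or on/after first dose; a start in the later year is new concomitant under any imputed month. Visits at Weeks 2, 4, 12, 24 and 28, with continuous AE monitoring, should usually allow an onset month to be established.

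What the reply does not remove is the contradiction inside 6.6.3 and the unstated precedence between 6.6.3 and 9.1.

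**Conclusion.** The point holds as an internal inconsistency with a conditional consequence. When the onset year is after the first-dose year, the month is missing and no earlier end date applies, SAP 6.6.3 always imputes a date outside the study (Day 336 to 367 against a limit of Day 204). That result rests only on the written rule and the visit schedule.

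The effect on TEAE counts is not demonstrated. It occurs only if the imputed date is tested ahead of the 9.1 fallback, and only where treatment ran into the later year. The 46% is the share of participants in whom that could arise under assumed uniform enrolment; it is not a rate of affected events. Using the Week 28 target instead gives 196/365 = 54%, but that measures follow-up crossing a year end and includes participants whose treatment had already ended, for whom the rule makes no difference to TEAE status. The documents give no basis for counting affected events, and they should be rare. This is a minor correction, worth making because it concerns safety data and costs little.

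**What to change.** Amend SAP 6.6.3 and 9.1 as follows:
- If the onset year is later than the first-dose year and the month is missing, impute 1 January of the onset year, no later than the event end date or last contact.
- If the years are equal, keep the current rule.
- State that end dates are imputed under 6.6.4 before onset dates under 6.6.3.
- State in 9.1 that the count-as-treatment-emergent rule is applied to the raw partial date and overrides any imputed date.

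The cost is one or two sentences of SAP text and a matching line in the programming specification. No data collection changes, and no other analysis is affected.
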